3.2 PROTOCOL DEVIATIONS

The number and percentage of patients with major and minor protocol deviations will be tabulated, by type (major/minor) and overall, and per class of deviation.

All available information concerning minor and major protocol deviations will be listed.

3.3 DEMOGRAPHIC AND OTHER BASELINE CHARACTERISTICS

3.3.1 *Available data*

The following parameters will be collected during the roll-over visit:

- Demographics: sex, women of childbearing potential, age (at signing of ICF of 2002), race, ethnicity, height, baseline weight, baseline body mass index, date of birth, date of signing informed consent form (ICF).
- Baseline disease characteristics: MG-ADL questionnaire (MG-ADL total score) at baseline (see 2.2.2), MG-QoL15r questionnaire (MG-QoL15r total score), EQ-5D-5L VAS score and AChR-Ab status (actual value from 2001 and 1704).

	Statistical Analysis Plan	
ARGX-113-2002	Final Analysis	Final 5.0 of 31Jan2025

3.3.2 *Derivation rules*

The following parameters will be derived:

- Age category: 18- <65 , ≥ 65 years
- Japanese vs non-Japanese: as defined in parent study protocol, from SDTM SUPPDM dataset of parent study.
- Region: Japan; US; rest of the world
- Baseline MG-ADL total score categories: <5 , 5-7, 8-9, ≥ 10
- Baseline eGFR category (derivation of eGFR is detailed in section 5.2.2):
 - Normal: ≥ 90 mL/min/1.73m²
 - Mildly impaired: 60 mL/min/1.73m² \leq eGFR < 90 mL/min/1.73m²
 - Moderately impaired: 30 mL/min/1.73m² \leq eGFR < 60 mL/min/1.73m²
 - Severely impaired: < 30 mL/min/1.73m²

Following subgroups are defined:

- AChR-Ab status: seropositive, seronegative
- Age category: 18- <65 years, ≥ 65 years
- Race: white, Asian, Other
- Region: United States, Japan, rest of the world
- Sex: male, female
- eGFR category at baseline: normal, mildly impaired, moderately impaired, severely impaired (as defined above)

3.3.3 *Presentation of results*

Demographics will be presented using descriptive statistics for age, height, weight and BMI and frequency tabulations for age category, sex at birth, race, region, ethnicity, Japanese/non-Japanese participants.

Baseline disease characteristics will be presented using descriptive statistics for baseline scores and a frequency tabulation for AChR-Ab status, baseline eGFR categories, and baseline MG-ADL total score categories.

Demographics and baseline disease characteristics tables will be generated by the subgroups mentioned above.

Demographics and baseline disease characteristics tables (except subgroup tables) will be repeated by average treatment duration per year.

All demographic data and baseline disease characteristics will be listed. The demographics listing will also show the date ICF for CTP v3.0 was signed, the average treatment duration per year (see section 2.4.3) and the time between first administration in the study and the first administration of the cycle wherein the ICF for protocol v3.0 was signed (see section 2.4.3).

	Statistical Analysis Plan	
ARGX-113-2002	Final Analysis	Final 5.0 of 31Jan2025

3.4 MEDICAL HISTORY AND CONCOMITANT DISEASES

Medical history and concomitant diseases are not collected in this open-label extension study. A separate listing will be created for hospitalizations.

3.5 PRIOR AND CONCOMITANT THERAPIES

3.5.1 *Available data*

All therapies are coded using the September 2021 version of the WHO-DRUG. ATC selection is performed. ATC coding up to level 4 is available in the clinical database. For each therapy, a start date or prior flag and stop date or ongoing flag are collected.

3.5.2 *Derivation rules*

Based on their start and stop date, therapies will be allocated to each analysis period during which they were administered. A therapy can therefore be reported in more than one analysis period.

Analysis periods are defined in section 2.2.1. Therapies with (partially) missing dates will be allocated to each period unless the available parts of the therapy start or stop date or prior and ongoing flags provide evidence the therapy was not taken during that period.

Concomitant therapies are defined as therapies taken on or after the first OLE dose date. Prior therapies are not in the scope of this interim analysis.

MG-specific therapies that were administered during the first year will be considered separately. First year is defined as the period starting from first dose in study 2002 until day 365 relative to first dose.

3.5.3 *Presentation of results*

Concomitant therapies will be tabulated, by ATC class (level 1 and level 3) and generic term. This table will be provided overall, not by cycle. The table for concomitant therapies will include MG therapies.

All concomitant therapies data will be listed with detailed information about ATC classes. Concomitant procedures will be listed separately.

For MG therapies during the first year, the number of participants per medication class (steroids, NSIDs and AChE inhibitors: appendix 9.3) and the combination of classes will be shown.

A separate listing will be created of participants receiving rescue medications. Rescue medications will be identified based on a flag on the SDTM data in the CM domain (Concomitant Medications).

Vaccination history will only be listed.

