6.8.4. Rescue Therapy

PLEX, Ig therapy, immunoabsorption, an increased dose of the current corticosteroid, or the use of a different corticosteroid used as a monotherapy or in combination with another therapy are considered rescue therapy if both of the following conditions apply:

1. The treating physician believes that the participant's health is in jeopardy if rescue therapy is not provided, and
2. The participant is deteriorating clinically according to the protocol-defined criteria, which includes at least 1 of the following:
 - a. new or worsening of respiratory/bulbar symptoms, or
 - b. at least a 2-point increase in any individual nonocular item on the MG-ADL scale compared to the previous visit

The date and time of rescue medication administration, and the name, dosage regimen, and response to the rescue medication will be recorded in the eCRF. Prior to administration of rescue therapy, the MG-ADL total score should be recorded if possible.

Participants who receive rescue therapy under the previously listed conditions will not be discontinued from the study unless rescue therapy is given in response to a life-threatening

situation. Participants may not receive PLEX, Ig therapy, or immunoabsorption more than 3 times per year. When rescue therapy is needed, what therapy was used and the response to that therapy must be documented in the eCRF. The MG-ADL total score will be used to measure the response to the therapy at the safety follow-up (SFU) visit.

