8.2 LISTINGS

GENERAL CHARACTERISTICS

16.2.1.1	Study and Treatment Discontinuation	RO
16.2.1.2	COVID-19-Related Comments	SAF
16.2.1.3	COVID-19-Related Remote Visits	SAF
16.2.2.1	Protocol Deviations	SAF
16.2.4.1	Demographic Data	SAF
16.2.4.2	Baseline Disease Characteristics	SAF
16.2.4.3	Concomitant Therapies	SAF
16.2.4.4	Concomitant Procedures	SAF
16.2.4.5	Rescue Therapies	SAF
16.2.4.6	Hospitalizations	SAF

Statistical Analysis Plan

ARGX-113-2002

Final Analysis

Final 5.0 of 31Jan2025

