9.3 MG THERAPIES AND PROCEDURES

Steroids	NSIDs	AChE inhibitors	Other	Procedures
PREDNISONE	CICLOSPORIN	NEOSTIGMINE	ECULIZUMAB	PLASMAPHERESIS
PREDNISOLONE	AZATHIOPRINE	NEOSTIGMINE BROMIDE	NIPOCALIMAB	THYMECTOMY
METHYL PREDNISOLONE	MYCOPHENOLATE MOFETIL	PYRIDOSTIGMINE	RITUXIMAB	ELECTRONEUROGRAPHY
HYDROCORTISONE	MYCOPHENOLATE SODIUM	PYRIDOSTIGMINE BROMIDE	IMMUNOGLOBULINS	FEEDING TUBE USER
TRIAMCINOLONE	MYCOPHENOLIC ACID	AMBENONIUM	IMMUNOGLOBULINS NOS	GASTROSTOMY ^a
DEFLAZACORT	METHOTREXATE	AMBENONIUM CHLORIDE	IMMUNOGLOBULIN THERAPY	ELECTROMYOGRAM
METHYL PREDNISOLONE SODIUM SUCCINATE	TACROLIMUS	DISTIGMINE	IMMUNOGLOBULIN HUMAN NORMAL	ENTERAL NUTRITION
PREDNISOLONE ACETATE	CYCLOPHOSPHAMIDE	DISTIGMINE BROMIDE	IMMUNOGLOBULIN G HUMAN	IMMUNOADSORPTION THERAPY
	CYTOPHOSPHANE			
	TACROLIMUS MONOHYDRATE			

^a Study physician will review case by case for this procedure to decide whether MG-related or not.

Statistical Analysis Plan

ARGX-113-2002

Final Analysis

Final 5.0 of 31Jan2025

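### The SAP's rule for identifying rescue, a flag in the concomitant-medication domain, does not ensure that plasma exchange and immunoadsorption given as rescue reach the rescue listing.

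*SAP*

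**What the plan says.** Protocol 6.8.4 counts the following as rescue when its two conditions are met: "PLEX, Ig therapy, immunoabsorption, an increased dose of the current corticosteroid, or the use of a different corticosteroid". Protocol 6.8.2 provides for plasma exchange, Ig therapy and immunoadsorption as rescue throughout the study, up to a yearly limit.

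SAP 3.5.3 plans one display: "A separate listing will be created of participants receiving rescue medications". It identifies the records by one rule: "Rescue medications will be identified based on a flag on the SDTM data in the CM domain (Concomitant Medications". No other domain or source is named. In SAP 8.2 the display is listing 16.2.4.5, titled "Rescue Therapies".

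SAP 3.5.3 also says "Concomitant procedures will be listed separately". SAP 8.2 has two such listings, 16.2.4.4 (Concomitant Procedures) and 16.2.4.8 (Procedures). Appendix 9.3 sorts MG treatments into columns. "PLASMAPHERESIS" and "IMMUNOADSORPTION THERAPY" stand under Procedures, whereas "IMMUNOGLOBULIN THERAPY" stands under Other and the corticosteroids have their own column.

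**The concern.** The rule looks in the medication data, but the SAP's own appendix treats two of the protocol's rescue therapies as procedures. A participant whose only rescue was plasma exchange or immunoadsorption could then be missing from the one listing meant to show rescue, and a reader would naturally take absence from that listing as absence of rescue.

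This matters for interpretation. SAP 4.1.2 and 4.1.3 summarise MG-ADL from observed data and describe no handling of rescue, so the rescue listing is the visible means of seeing whose scores follow rescue. A procedure row without a rescue label does not show that the two conditions of protocol 6.8.4 were met.

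**Working it through.** The plan states no figure on this point. The check maps each therapy in protocol 6.8.4 to its column in SAP Appendix 9.3, and asks whether the rule in SAP 3.5.3 is certain to reach it.

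| Rescue therapy (protocol 6.8.4) | Column in SAP 9.3 | Reached by a flag in the CM domain? |
|---|---|---|
| Ig therapy | Other (immunoglobulin terms) | Yes |
| Increased dose of current corticosteroid | Steroids | Yes |
| Different corticosteroid | Steroids | Yes |
| Plasma exchange | Procedures (plasmapheresis) | Only if also entered and flagged in CM |
| Immunoadsorption | Procedures | Only if also entered and flagged in CM |

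Yes here assumes that the site's rescue flag is set correctly.

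- Certain coverage: 5 − 2 = 3 of 5 therapies.
- Possible coverage: 3 + 0 = 3 to 3 + 2 = 5 of 5.
- Coverage if procedure records were also used: 5 of 5.

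Three other places support reading the two therapies as procedures rather than medications:

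1. SAP 3.5.1 codes therapies with WHO-DRUG, a drug dictionary.
2. SAP 3.5.3 and SAP 8.2 keep procedures in listings of their own.
3. The IgG sensitivity analysis in SAP 4.4.3 names an immunoglobulin-related MG therapy and a plasmapheresis procedure as two separate triggers. Where the SAP needed both kinds of record it named both; the rescue rule names one.

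Coverage of therapies is not coverage of participants. Let p be the share of rescued participants whose only rescue was plasma exchange or immunoadsorption, and c the share of those who also have a flagged CM record of it. The share missing from the listing is p × (1 − c). Neither p nor c is in the documents. If c = 1 the result is 0 whatever p is; if c = 0 it equals p. The documents alone allow any value from 0 to 1, so no percentage can be given.

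A search of the visible outputs in SAP 8.1 and 8.2 finds no rescue table and no rescue listing other than 16.2.4.5.

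**The case against.** The strongest reply is that a wording gap is being read as a data loss. Appendix 9.3 groups terms; it does not assign SDTM domains. Protocol 6.8.4, having named plasma exchange and immunoadsorption, has sites record the rescue medication in the eCRF, so that term seems to cover the whole set and a rescue form feeding CM is possible. The listing's title also says therapies. This stands. A reader might infer that the listing omits two therapies or under-reports rescue, but the documents do not say that these records are absent from CM. They support only that the rule does not ensure capture.

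A second reply is that little depends on the listing. This also largely stands:

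- A reader might infer that an endpoint is biased. No visible endpoint, table or denominator uses the rescue flag, and the IgG sensitivity analysis handles plasmapheresis without it.
- A reader might infer that the limit on rescue or the discontinuation rule (protocol 6.8.4 and 7.2) is put at risk. Those rules are applied during conduct, and SAP 3.1 tabulates and lists discontinuations and their reasons independently.
- A reader might treat the listing as the plan's measure of treatment failure. The protocol defines treatment failure only by MG-ADL change, for eligibility from study ARGX-113-1705 (protocol 5.1).
- The procedures themselves are listed in 16.2.4.4 and 16.2.4.8. Their columns are not specified, so the lack of a rescue label means that none is described.

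A third reply is that tables 14.2.3.1 to 14.2.3.4 and SAP 4.2 are redacted, so the claim about the only rescue output can cover only what is visible. That is correct.

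What remains is that a stated rule, read with the SAP's own classification, points at a source that need not hold two of the five therapies, and nothing in the SAP closes the gap.

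**Conclusion.** The point holds as a gap in how rescue is identified. The rule is certain to reach 3 of 5 rescue therapies and may reach 3 to 5. Listing 16.2.4.5 may fail to show participants rescued by plasma exchange or immunoadsorption alone. A participant who also had a flagged steroid or immunoglobulin rescue would still appear, though the procedure might not.

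The conclusion assumes that Appendix 9.3 reflects how these treatments are recorded. If rescue procedures are entered and flagged in CM, the listing is complete and only the wording needs repair. Because the documents do not settle this, confidence is medium. The effect is confined to a descriptive listing, but the change should be made because that listing is the only visible rescue output.

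**What to change.** In SAP 3.5.3, define rescue therapies from two sources: flagged CM records, and on-study procedure records of plasmapheresis or plasma exchange and of immunoadsorption. Name the domains and the flag variable. Build listing 16.2.4.5 from the union, and use the term rescue therapies throughout in place of rescue medications.

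The procedure records can be used even if they carry no rescue flag, because protocol 6.8.2 provides for these two treatments only as rescue. A procedure record alone does not show that both conditions of protocol 6.8.4 were met, so the listing should show which source each record came from.

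The cost is a few lines of SAP text and the combination of records that the SAP already plans to list. If CM already holds these records, one sentence saying so is enough. No additional data collection and no change to any clinical rule is involved.

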3.6 STUDY DRUG ADMINISTRATION

3.6.1 *Available data*

For each study drug administration, the start and end date/times and the volumes will be recorded, as well as data on self-administration.

	Statistical Analysis Plan	
ARGX-113-2002	Final Analysis	Final 5.0 of 31Jan2025

3.6.2 *Derivation rules*

The following parameters will be derived:

- Number of administrations: number and percentage of patients who had 1, 2, etc. administrations (in decreasing order) per treatment cycle and overall.
- Compliance (%) per treatment cycle: $100 * (\text{number of doses received} / \text{number of doses expected})$. For completed cycles, the expected number of doses is 4; for the last cycle of ongoing participants, the number of expected doses is based on the number of treatment visits performed.
- Actual dose (mg): Actual total volume of IMP extracted from the vials (mL) * █ mg/mL per administration.
If the question: 'Was the correct volume administered as per protocol?' is answered as 'Yes', the actual dose will be set to 1000 mg.
- Actual dose for EFG SC per administration, using categories < 900 mg, and 900-1000 mg

3.6.3 *Presentation of results*

A frequency table for the number of administrations per cycle and overall, and the actual dose per administration will be created.

Descriptive statistics of the overall number of administrations and treatment compliance.

In addition, a frequency tabulation will be provided showing:

- Number and percentage of participants who performed self-administration at home or onsite, or caregivers who administered the injection to the participant at home or onsite over time by cycle.
- Number of training visits needed for the participant or caregiver to be competent to start administering efgartigimod PH20 SC. This is defined by the number of trainings received in study 2002 until the first visit where patient/caregiver is considered adequately trained (collected in FA dataset). When both staff demonstration and self-administration under supervision occurs at the same visit, this visit is considered as 1 training. For participants already considered as adequately trained in study 2001, the number of training visits needed is set to zero.
- Number and percentage of self- or caregiver-supported study drug administration at home across participants and cycles. The denominator is the total number of treatment visits in the study.

All study drug administration data and self-administration will be listed.

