6.1. Study Intervention(s) Administered

Table 5: Study Intervention Administered

Treatment Group	Efgartigimod PH20 SC
Intervention name	Efgartigimod solution for SC injection █ mg/mL coformulated with rHuPH20
Type	Biologic
Dose formulation	Efgartigimod drug product of █ mg/mL for a fixed dose of 1000 mg for SC injection coformulated with █ U/mL rHuPH20
Unit dose strength(s)	█ mg/mL
Dosage level(s)	1000 mg q7d for a total of 4 injections in a TP, with multiple TPs possible depending on clinical effect
Route of administration	SC injection
Use	Investigational
IMP and NIMP	IMP
Sourcing	Provided centrally by the sponsor
Packaging and labeling	The IMP will be provided in glass vials and will be packed and labeled in secondary boxes. Each glass vial and box will be labeled as per country requirement.

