6.7. Treatment of Overdose

For this study, a variation of less than 10% of the amount of efgartigimod PH20 SC that should be injected for each administration will not be considered an overdose or medication error. A variation of greater than 10% of the intended amount of efgartigimod PH20 SC will be considered a medication error and an overdose, if applicable, regardless of whether any AEs occur.

An overdose is defined as a deliberate or accidental administration of IMP to a participant at a dose more than 10% that was assigned to that participant per the study protocol.

A medication error is any preventable incident that may cause or lead to inappropriate IMP use or participant harm while the IMP is in the care of the health care professionals. Such an incident may be due to health care professional practice, product labeling, packaging and preparation, administration procedures, and/or systems, including prescribing, order communication, nomenclature, compounding, dispensing, distribution, administration, education, monitoring, and/or use.

In case of a suspected overdose and/or medication error, the participant must be treated according to standard medical practice based on the investigator's judgment. The suspected overdose and/or medication error must be documented, with the quantity of the excess dose, as well as any observed AEs that are associated with the overdose.

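### Actual dose for administrations not confirmed as correct is derived from the volume drawn up, so a partial injection can be tabulated as 900-1000 mg

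*SAP*

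**What the plan says.** SAP 3.6.1 describes the data collected at each administration: "the start and end date/times and the volumes will be recorded". It does not say whether these are volumes drawn up, volumes injected, or both.

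SAP 3.6.2 then gives two rules for the actual dose. The general formula multiplies the concentration (redacted) by a volume defined as "Actual total volume of IMP extracted from the vials (mL". An override follows: "If the question: 'Was the correct volume administered as per protocol?' is answered as 'Yes', the actual dose will be set to 1000 mg". No separate rule is given for a 'No' or blank answer, so the extraction formula applies to those records.

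The result is reported as "Actual dose for EFG SC per administration, using categories < 900 mg, and 900-1000 mg". SAP 3.6.3 plans a frequency table, listed as 14.1.2.6 for the safety analysis set and 14.1.2.6B by average treatment duration in the modified set.

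Protocol 6.1 describes the product as supplied "for a fixed dose of 1000 mg for SC injection coformulated with" rHuPH20. Protocol 6.7 sets its tolerance for dose variation as "a variation of less than 10% of the amount of efgartigimod PH20 SC that should be injected for each administration".

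**The concern.** The override asks about the volume administered, while the formula uses the volume extracted. The two differ when an injection is stopped, leaks or is left incomplete after the syringe has been filled. Such an administration should be answered 'No', and 'No' is the branch that goes back to the extracted volume. The formula therefore decides the result only for records not confirmed as correct, and there it can return the value of a correct dose.

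Actual dose is the only planned tabulation of the amount delivered. Compliance in SAP 3.6.2 counts doses and takes no account of milligrams. At stake is whether the exposure table places a known-incorrect administration in the right dose category.

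**Working it through.** **Inputs**
- Planned dose: 1000 mg per injection (Protocol 6.1).
- Dose categories: below 900 mg, and 900-1000 mg (SAP 3.6.2).
- Concentration c: redacted. The full volume is 1000/c mL, so c cancels.
- Drawn fraction f and injected fraction g of the full volume, with g no larger than f. The values below are illustrative assumptions.

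**Formulas**
- SAP, answer 'Yes': dose = 1000 mg.
- SAP, any other answer: dose = f x (1000/c) x c = 1000f mg.
- Dose from the injected volume: g x (1000/c) x c = 1000g mg.

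**Reproducing the plan's figure.** With f = 1 the extraction formula gives 1000 x 1 = 1000 mg, the same as the override. After a full draw, both branches give one value, and g appears in neither.

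**Comparison**

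| Drawn f | Injected g | Answer | SAP dose and category | Injected dose and category |
|---|---|---|---|---|
| 1.00 | 1.00 | Yes | 1000 mg, 900-1000 | 1000 mg, 900-1000 |
| 1.00 | 0.92 | No | 1000 mg, 900-1000 | 920 mg, 900-1000 |
| 1.00 | 0.89 | No | 1000 mg, 900-1000 | 890 mg, <900 |
| 1.00 | 0.50 | No | 1000 mg, 900-1000 | 500 mg, <900 |
| 1.00 | 0.10 | No | 1000 mg, 900-1000 | 100 mg, <900 |
| 0.95 | 0.50 | No | 950 mg, 900-1000 | 500 mg, <900 |
| 0.85 | 0.50 | No | 850 mg, <900 | 500 mg, <900 |
| 1.05 | 0.50 | No | 1050 mg, no category | 500 mg, <900 |

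**Reading the table.** A record not answered 'Yes' is put in the wrong category when f is between 0.90 and 1.00 and g is below 0.90. When f is below 0.90 the category is right even if the milligram value is too high, because the injected amount cannot exceed the extracted amount. When g is between 0.90 and 1.00 after a full draw, the dose is overstated but the category is right. A draw above nominal gives a value for which the SAP has no category.

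**Relation to the protocol tolerance.** 1000 x (1 - 0.10) = 900 mg, so the SAP cut-off coincides numerically with the 10% limit in Protocol 6.7, which is framed on the amount to be injected.

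**The case against.** Several points on the other side carry weight.

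- **The CRF is not among the documents.** The extraction wording may be a field label, and how sites complete it for an interrupted injection is unknown. This stands. It limits what can be said about the data, but the rule as written still does not use the injected amount.
- **A reader might infer that the table cannot detect underdosing at all.** The documents do not support that. Every draw below 90% of the full volume is correctly placed under 900 mg.
- **A reader might infer that the self-administration results would be biased.** They would not be. The feasibility endpoints count who administered at home, the training visits needed, and the share of self- or caregiver-supported administrations. None uses milligrams. No safety, efficacy, PK or PD endpoint uses this variable, and the treatment-duration groups rest on cycle counts and dates.
- **A reader might infer that partial injections would be hidden.** They would not be. All administration data go into Listing 16.2.5.1. Protocol 6.4 requires deviations from the intended regimen to be recorded in the administration log and eCRF, and such cases may also appear in the protocol deviation table (14.1.1.12).
- **Protocol 6.7 does not conflict with the SAP.** It defines overdose and medication error and does not prescribe how exposure is derived. This stands. The matching 900 mg figure makes the injected amount the natural basis for the table, but the protocol does not require it.

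None of this changes the category assigned to a near-full draw that was only partly injected.

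**Conclusion.** The point holds as a limited derivation error. For records not answered 'Yes', SAP 3.6.2 returns a dose that does not depend on what was injected. After a draw of 90% to 100% of the full volume, it reports 900-1000 mg even if far less was given. Tables 14.1.2.6 and 14.1.2.6B can therefore show a known-incorrect administration as a full dose, and no other planned tabulation of the amount delivered corrects this.

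The consequence is confined to one descriptive exposure display. The number of affected records cannot be derived from the documents and may be small or zero. A reader might try an estimate: 201 x an assumed 40 doses = 8,040 administrations, of which an assumed 0.5% to 2% answered 'No' gives about 40 to 161. That should not be used. Neither the 40 doses nor the rate is in the documents, 201 is an upper limit on enrolment, and the result counts every 'No' record, including short draws that the rule classifies correctly.

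The conclusion assumes that the SAP text is programmed literally and that a partial injection is answered 'No'.

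**What to change.** Amend the actual-dose rule in SAP 3.6.2 for records not answered 'Yes':

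1. If the CRF captured the injected volume, use injected volume x concentration.
2. If only the extracted volume is available and the extracted dose is below 900 mg, keep the record under 900 mg. Underdosing is certain there and should not be moved to an unknown category.
3. If only the extracted volume is available and the extracted dose is 900 mg or more, place the record in a separate category, 'incorrect volume reported, amount injected unknown', instead of 900-1000 mg. This also takes in draws above nominal, which have no category now.
4. Report the number of 'No' answers in the same table, with any blank answers counted separately.

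This version needs no measurement of lost or leaked volume. That matters because the SAP is dated 31 January 2025 and study participation ran at the latest to 31 December 2024, so the rule has to work with data already collected.

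The cost is a revised derivation, one extra category and a count in Tables 14.1.2.6 and 14.1.2.6B. The reported number of full-dose administrations may fall slightly, and some of the records moved may have received nearly the full dose.

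### The actual-dose table has no category for derived doses above 1000 mg, although the protocol's 10% limit runs in both directions

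*SAP*

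**What the plan says.** SAP 3.6.2 derives the actual dose per administration in two ways. By default it takes "Actual total volume of IMP extracted from the vials (mL") and multiplies by the concentration, which is redacted. No upper cap is stated. If the CRF question on whether the volume given was correct is answered yes, "the actual dose will be set to 1000 mg".

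The same section then sets the grouping: "Actual dose for EFG SC per administration, using categories < 900 mg, and 900-1000 mg". SAP 3.6.3 says where it is used: "A frequency table for the number of administrations per cycle and overall, and the actual dose per administration will be created". In the list of tables (SAP 8.1) the matching entries are Table 14.1.2.6 (safety analysis set) and Table 14.1.2.6B (modified safety analysis set, by average treatment duration per year).

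Protocol 6.1 gives the dosage as "1000 mg q7d for a total of 4 injections in a TP". Protocol 6.7 sets the tolerance: "a variation of less than 10% of the amount of efgartigimod PH20 SC that should be injected" counts as neither an overdose nor a medication error. Beyond it, "A variation of greater than 10% of the intended amount of efgartigimod PH20 SC will be considered a medication error and an overdose, if applicable". It adds: "An overdose is defined as a deliberate or accidental administration of IMP to a participant at a dose more than 10% that was assigned".

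**The concern.** The protocol's rule has two sides and the SAP's grouping has one. The 900 mg cut is the protocol's lower limit, but the grouping stops at the nominal dose instead of continuing to the upper limit and beyond. A derived dose above 1000 mg therefore belongs to no row, whether it is a small excess that the protocol tolerates or an amount beyond its overdose limit.

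The SAP does not say what to do with such a record. It could stay in the denominator with no row, so that the percentages fall short of 100%. It could be treated as missing and leave the denominator too, because SAP 2.4.1 excludes missing values from percentages. Or it could be placed in 900-1000 mg and read as an in-range dose.

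This matters because long-term safety is the primary objective and feasibility of self-administration is a secondary one. Trained participants or caregivers may give doses at home after the first dose of a treatment period, subject to the protocol's on-site requirements. The exposure table is where a reader would look for how often the amount differed from plan. Table 14.1.2.6B also belongs to the analyses meant to compare groups with increased exposure (SAP 2.4.3).

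**Working it through.** The plan states no figure to reproduce. The check is whether the categories cover every value the derivation can produce.

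**Inputs.** Assigned dose 1000 mg (protocol 6.1); 10% limit (protocol 6.7); derivation and categories (SAP 3.6.2).

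**Protocol limits in mg.**
- Lower: 1000 × (1 − 0.10) = 900 mg.
- Upper: 1000 × (1 + 0.10) = 1100 mg.

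The overdose definition omits a word after the percentage. It is read here as more than 10% above the assigned dose, that is, above 1100 mg. The protocol does not classify a variation of exactly 10%.

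**SAP rule.** If the volume is marked correct, dose = 1000 mg. Otherwise dose = extracted volume × concentration. Then assign to <900 or 900-1000.

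| Marked correct volume | Dose from extracted volume (mg) | Dose used (mg) | SAP category |
|---|---|---|---|
| Yes | 1000 | 1000 | 900-1000 |
| Yes | 1050 | 1000 | 900-1000 |
| No | 850 | 850 | <900 |
| No | 900, 950, 1000 | unchanged | 900-1000 |
| No | 1001, 1050, 1100 | unchanged | none |
| No | 1101, 2000 | unchanged | none |

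The categories cover everything up to 1000 mg and nothing above it. Two different kinds of record are left out: doses above 1000 mg and up to 1100 mg, within or exactly at the protocol's limit, and doses above 1100 mg, beyond it.

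**Do other planned summaries fill the gap?**
- Compliance (SAP 3.6.2) is doses received over doses expected. It counts administrations, not mg, so an excess dose scores as one dose.
- Descriptive statistics in SAP 3.6.3 are planned for number of administrations and compliance. No mean or maximum of actual dose is mentioned.
- Average treatment duration per year (SAP 2.4.3) is built from cycle counts and dates, not from mg.
- Under protocol 10.4.1 an overdose is not itself an adverse event unless intentional with possible self-harm intent. Its signs, symptoms and sequelae are collected, so the AE tables would show consequences but not the excess dose.
- Protocol deviations are tabulated by type and class (SAP 3.2, Table 14.1.1.12), but neither document says that overdose or dosing error is a class.
- SAP 8.1 lists no overdose or medication-error table.

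**The case against.** The strongest reply is that little is lost. All administration data are listed (SAP 3.6.3, Listing 16.2.5.1). Protocol 6.7 requires the excess quantity to be documented, protocol 6.4 has deviations from the regimen recorded in the log and eCRF, and deviations are tabulated and listed. The table is descriptive, in a single-arm study with no hypotheses. An unclassified dose might also be noticed when the table is reviewed. All of this stands, and it limits the point to summary reporting.

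Three further limits also stand.
- The override means that not every administration above 1000 mg is unclassified. One marked as correct volume is counted as 1000 mg. A true overdose should not be marked that way, so the override should not remove the gap for those records.
- Extracted volume is not the same as injected dose. Protocol 6.7 defines overdose by what is administered, so a row above 1100 mg would not be a strict count of protocol overdoses.
- The concentration is redacted and the vial fill volume is not given. A reader cannot tell how easily one administration could exceed 1000 mg, or whether the presentation explains the 1000 mg ceiling.

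A reader might infer that the trial's safety reporting cannot show overdoses at all. The documents do not support that, given the listings, the deviation outputs and the collection of clinical sequelae. Nor do they support a numerical estimate of affected records: they give no dosing-error rate and no frequency of home preparation.

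What the reply does not do is make the categories exhaustive, or point to another planned table specified to show doses above 1000 mg.

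**Conclusion.** The point holds in a limited form. Followed exactly, SAP 3.6.2 leaves any derived dose above 1000 mg without a row in the actual-dose frequency tables, although the protocol applies its 10% limit in both directions. The defect is in the summary and not in data capture. No hypothesis test, sample size or efficacy result depends on it.

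Its size cannot be determined from the documents and may be zero. The conclusion rests on three readings: that Tables 14.1.2.6 and 14.1.2.6B carry the actual-dose grouping, as their titles and SAP 3.6.3 indicate; that the overdose definition means more than 10% above the assigned dose; and that no unstated cap is applied in programming. It is worth correcting because the stated rule misreports the upper side of exposure whenever such a record exists. If none exists, a zero in the added row is itself informative.

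**What to change.** In SAP 3.6.2, replace the two categories with an exhaustive set built on the protocol's existing limits: <900, 900-1100 and >1100 mg. If the sponsor wants to keep the present row, use <900, 900-1000, >1000-1100 and >1100 mg. Apply the set to Tables 14.1.2.6 and 14.1.2.6B.

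Report the number of participants with at least one administration in each outer category, alongside the count of administrations.

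Add a footnote saying that the dose is based on the volume extracted from the vials, and that records marked as correct volume are set to 1000 mg. The top row will then not be read as a strict count of protocol overdoses.

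Record the change in SAP section 6. The cost is one or two extra rows and a footnote, using data already collected. It changes no dose or clinical rule. This is a free improvement.
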